3.5.2.1 Vs-Screening [day -42 to -3]

The procedures listed below will be performed sequentially over a period of 42 to 3 days prior to the baseline visit (Week 0). The sequence is specified in the Schedule of Assessments (section 3.5.1).

- Subject's decisional capacity to consent: MacCAT-CR interview (in the Netherlands). To be performed prior to the informed consent signature.
- Subject information and consent discussion
- Written informed consent from the subject
- Written informed consent from the caregiver
- Year of birth
- Gender
- Ethnic origin
- Women of child bearing potential: discussion on reliable contraceptive measures (refer to section 4.2.3)
- Report former brain MRI assessment (<1 year)
- Year of onset of disease
- Familial history for AD
- Previous medications for AD (describe)
- Relevant medical and surgical history for other diseases
- Prior medications
- AEs
- Review NIA-AA diagnostic criteria
- Cognition: MMSE, RBANS (form C)
- Clinical status: C-SSRS, CDR
- Physical and neurological examination
- Vital signs
- Blood sample collected for:
 - routine hematology and biochemistry evaluation, including CRP
 - antibody response components including for example anti-pTau and anti-Tau IgG and IgM titers
 - Inflammatory cytokines
 - coagulation indices assessment
 - screening tests: B12, folate, thyroid function tests, HIV, Hepatitis B and C and VDRL (syphilis serology), ApoE genotyping, serum pregnancy testing ANA and anti-dsDNA testing

- Routine urine evaluation
- ECG
- Brain MRI
- Lumbar puncture for cerebrospinal fluid sample (12 mL) for cell count, inflammatory markers, exploratory biomarker testing and for confirming amyloid and Tau positivity according to inclusion criteria (note: blood for serum albumin should be taken and measured concomitantly).
- Review inclusion and exclusion criteria

3.5.2.1.1 *Re-screening:*

If a subject has entered a screening period and is considered eligible for the study but cannot be randomized in one sub-cohort for logistical reasons (e.g., due to completion of randomization in current sub-cohort(s)), the subject may be re-screened at a later time for potential randomization in subsequent sub-cohorts in the study.

In such cases, the following screening assessments should be re-done over a period of 42 to 3 days prior to the baseline visit (Week 0) to re-confirm eligibility, i.e.:

- Subject's decisional capacity to consent: MacCAT-CR interview (in the Netherlands). To be performed prior to the informed consent signature.
- Subject information and consent discussion
- Written informed consent from the subject
- Written informed consent from the caregiver
- Women of child bearing potential: discussion on reliable contraceptive measures (refer to section 4.2.3)
- Report former brain MRI assessment (<1 year)
- Previous medications for AD (describe)
- Relevant medical and surgical history for other diseases
- Prior medications
- AEs
- Review NIA-AA diagnostic criteria
- Cognition: MMSE, RBANS (form C)
- Clinical status: C-SSRS, CDR
- Physical and neurological examination
- Vital signs
- Blood sample collected for all lab tests applicable to Screening visit except ApoE genotyping
- Routine urine evaluation
- ECG
- Brain MRI should be repeated if clinically indicated (e.g. abnormality on neurological exam) or if the MRI scan from the preceding screening period is more than 6 months prior to re-screening
- Lumbar puncture for cerebrospinal fluid sample (12 mL) should be repeated if the procedure from the preceding screening period is more than 6 months before rescreening
- Review inclusion and exclusion criteria

3.5.2.2 Visit 1/ Baseline [Week 0]

- Check that inclusion/exclusion criteria are still applicable
- Subject and caregiver training to report any AE and SAE
- AEs
- Concomitant medications (describe new and/or changes from the previous visit)

C AC Immune

- Physical and neurological examination
- Vital signs before the administration of study medication
- Cognition: RBANS (form A)
- Clinical status: CDR (only applicable to sub-cohort 1.1), NPI, C-SSRS
- Blood sample collected prior to administration of study medication for:
 - routine hematology and biochemistry evaluation, including CRP
 - antibody response components including for example anti-pTau and anti-Tau IgG and IgM titers
 - Inflammatory cytokines
 - AD biomarker assessment
 - T-Cell profile assessment
 - ANA and anti-dsDNA testing
- Routine urine evaluation and urinary pregnancy test
- Administration of study medication
- 24-hour clinical observation:
 - Vital signs and observation of injection site 1, 2, 4, 8, 12 and 24 hours after the administration of study medication
 - Physical examination before discharge

3.5.2.3 Phone call 1 [Week 0]

- AEs
- Concomitant medications (describe new and/or changes from the previous visit)
- In case of safety concerns, as per investigator assessment, an additional visit will be scheduled in order to further assess the event(s).

3.5.2.4 Visit 2 [Week 2]

- AEs
- Concomitant medications (describe new and/or changes from the previous visit)
- Physical and neurological examination
- Vital signs
- Blood sample collected for:
 - routine hematology and biochemistry evaluation, including CRP
 - antibody response components including for example anti-pTau and anti-Tau IgG and IgM titers
 - Inflammatory cytokines
 - AD biomarker assessment
 - ANA and anti-dsDNA testing
- Routine urine evaluation

3.5.2.5 Visit 3 [Week 8]

- AEs
- Concomitant medications (describe new and/or changes from the previous visit)
- Physical and neurological examination
- Vital signs before the administration of study medication
- Blood sample collected prior to administration of study medication for:
 - routine hematology and biochemistry evaluation, including CRP
 - antibody response components including for example anti-pTau and anti-Tau IgG and IgM titers
 - Inflammatory cytokines

AD biomarker assessment

ANA and anti-dsDNA testing

- Routine urine evaluation and urinary pregnancy test
- Administration of study medication
- 4-hour clinical observation:
 - Vital signs and observation of the injection site 1, 2 and 4 hours after the administration of study medication
 - o Physical examination before discharge

3.5.2.6 Phone call 2 [week 8]

- AEs
- Concomitant medications (describe new and/or changes from the previous visit)
- In case of safety concerns, as per investigator assessment, an additional visit will be scheduled in order to further assess the event(s).

3.5.2.7 Visit 4 [Week 10]

This visit can take place within a period of up to 2 days.

- AEs
- Concomitant medications (describe new and/or changes from the previous visit)
- Physical and neurological examination
- Vital signs
- Blood sample collected for:
 - routine hematology and biochemistry evaluation, including CRP
 - antibody response components including for example anti-pTau and anti-Tau IgG and IgM titers
 - Inflammatory cytokines
 - AD biomarker assessment
 - ANA and anti-dsDNA testing
- Routine urine evaluation
- Brain MRI

3.5.2.8 Visit 4.1 [Week 15]

This visit is only applicable in future sub-cohorts or in ongoing sub-cohorts, in subjects not having yet reached this visit timepoint. If feasible, agreed with subject and locally permitted, these visits may also be performed at subject's home.

- AEs

- Concomitant medications (describe new and/or changes from the previous visit)
- Blood samples collected for:

antibody response components including for example anti-pTau and anti-Tau IgG and IgM titers

AD biomarker assessment

3.5.2.9 Visit 4.2 [Week 20]

This visit is only applicable in future sub-cohorts or in ongoing sub-cohorts, in subjects not having yet reached this visit timepoint. If feasible, agreed with subject and locally permitted, these visits may also be performed at subject's home.

- AEs
- Concomitant medications (describe new and/or changes from the previous visit)
- Blood samples collected for:

antibody response components including for example anti-pTau and anti-Tau IgG and IgM titers

AD biomarker assessment

3.5.2.10 Visit 5 [Week 24]

- Assessment of the subject's decisional capacity: MacCAT-CR interview (in the Netherlands)
- AEs
- Concomitant medications (describe new and/or changes from the previous visit)
- Physical and neurological examination
- Vital signs before the administration of study medication
- Blood sample collected prior to administration of study medication for: routine hematology and biochemistry evaluation, including CRP
 - antibody response components including for example anti-pTau and anti-Tau IgG and IgM titers
 - coagulation indices assessment
 - Inflammatory cytokines
 - AD biomarker assessment
 - ANA and anti-dsDNA testing
- Routine urine evaluation and urinary pregnancy test
- Administration of study medication
- 4-hour clinical observation:
 - Vital signs and observation of the injection site 1, 2 and 4 hours after the administration of study medication
 - Physical examination before discharge

Due to the Covid-19 pandemic, local travel restrictions in Finland effective as of 18 March 2020, and the need to preserve the safety of study participants, changes are made to the schedule of visits and procedures of sub-cohort 1.1 subjects:

- Given that the situation is not anticipated to be resolved to allow all procedures to be performed according to the protocol, Visit 5 will not be performed for any sub-cohort 1.1 subjects for whom the planned Visit 5 falls during the at-risk period.
- Instead, a remote visit will be performed in which the subject and caregiver are interviewed by telephone concerning any adverse events or changes in concomitant medications. Where possible, the NPI and C-SSRS scales will be administered during this interview. The remote visit will be performed at the initially planned Visit 5 date and according to the timewindow defined in the Schedule of Assessments, i.e. at week 24 ± 7 days.
- This change is not applicable to the subject who had Visit 5 (week 24) procedures according to the protocol on 18 February 2020.

3.5.2.11 Phone call 3 [Week 24]

- AEs
- Concomitant medications (describe new and/or changes from the previous visit)
- In case of safety concerns, as per investigator assessment, an additional visit will be scheduled in order to further assess the event(s).

Due to the Covid-19 pandemic, local travel restrictions in Finland effective as of 18 March 2020, and the need to preserve the safety of study participants, changes are made to the schedule of visits and procedures of sub-cohort 1.1 subjects: Phone call 3 is not applicable in case Visit 5 and the associated immunization have not been performed.

3.5.2.12 Visit 6 [Week 26]

This visit can take place within a period of up to 2 days.

- AEs
- Concomitant medications (describe new and/or changes from the previous visit)
- Physical and neurological examination
- Vital signs
- Cognition: RBANS (form B)
- Clinical status: CDR, NPI, C-SSRS
- Blood sample collected for:
 - routine hematology and biochemistry evaluation, including CRP
 - antibody response components including for example anti-pTau and anti-Tau IgG and IgM titers
 - Inflammatory cytokines
 - AD biomarker assessment
 - T-Cell profile assessment
 - ANA and anti-dsDNA testing
- Lumbar puncture for cerebrospinal fluid sample (12 mL) for cell count, inflammatory markers and exploratory biomarker testing (note: blood for serum albumin should be taken and measured concomitantly)
- Routine urine evaluation
- Brain MRI
- ECG

Due to the Covid-19 pandemic, local travel restrictions in Finland effective as of 18 March 2020, and the need to preserve the safety of study participants, changes are made to the schedule of visits and procedures of sub-cohort 1.1 subjects:

- Given that the situation is not anticipated to be resolved to allow all procedures to be performed according to the protocol, Visit 6 will not be performed for any sub-cohort 1.1 subjects for whom the planned Visit 6 falls during the at-risk period.
- Instead, a remote visit will be performed in which the subject and caregiver are interviewed by telephone concerning any adverse events or changes in concomitant medications. Where possible, the CDR, NPI and C-SSRS scales will be administered during this interview. The remote visit will be performed at the initially planned Visit 6 date and according to the time-window defined in the Schedule of Assessments, i.e. at week 26 ± 2 days.
- This change is not applicable to the subject who had Visit 5 (week 24) procedures according to the protocol on 18 February 2020.

3.5.2.13 Visit 6.1 [Week 31]

This visit is only applicable in future sub-cohorts or in ongoing sub-cohorts, in subjects not having yet reached this visit timepoint. If feasible, agreed with subject and locally permitted, these visits may also be performed at subject's home.

- AEs
- Concomitant medications (describe new and/or changes from the previous visit)
- Blood samples collected for:
 - antibody response components including for example anti-pTau and anti-Tau IgG and IgM titers
 - AD biomarker assessment

3.5.2.14 Visit 7 [Week 36]

- AEs
- Concomitant medications (describe new and/or changes from the previous visit)
- Physical and neurological examination
- Vital signs
- Blood sample collected for:
 - routine hematology and biochemistry evaluation, including CRP
 - antibody response components including for example anti-pTau and anti-Tau IgG and IgM titers
 - Inflammatory cytokines
 - AD biomarker assessment
 - ANA and anti-dsDNA testing
- Routine urine evaluation

Due to the Covid-19 pandemic, local travel restrictions in Finland effective as of 18 March 2020, and the need to preserve the safety of study participants, changes are made to the schedule of visits and procedures of sub-cohort 1.1 subjects:

- In case the situation is anticipated to not be resolved to allow all procedures to be performed according to the protocol, Visit 7 will not be performed. The decision will be taken on a caseby-case basis depending whether the visit for a particular subject is falling during the at-risk period.
- Instead, a remote visit will be performed in which the subject and caregiver are interviewed by telephone concerning any adverse events or changes in concomitant medications. Where possible, the NPI and C-SSRS scales will be administered during this interview. The remote visit will be performed at the initially planned Visit 7 date and according to the timewindow defined in the Schedule of Assessments, i.e. at week 36 ± 3 days.

3.5.2.15 Visit 7.1 [Week 42]

This visit is only applicable in future sub-cohorts or in ongoing sub-cohorts, in subjects not having yet reached this visit timepoint. If feasible, agreed with subject and locally permitted, these visits may also be performed at subject's home.

- AEs
- Concomitant medications (describe new and/or changes from the previous visit)
- Blood samples collected for:
 - antibody response components including for example anti-pTau and anti-Tau IgG and IgM titers
 - AD biomarker assessment

3.5.2.16 Visit 8 [Week 48]

- Assessment of the subject's decisional capacity: MacCAT-CR interview (in the Netherlands)
- AEs
- Concomitant medications (describe new and/or changes from the previous visit)
- Physical and neurological examination
- Vital signs before the administration of study medication
- Blood sample collected prior to administration of study medication for:
 - routine hematology and biochemistry evaluation, including CRP
 - antibody response components including for example anti-pTau and anti-Tau IgG and IgM titers

coagulation indices assessment

Inflammatory cytokines

AD biomarker assessment

- ANA and anti-dsDNA testing
- Routine urine evaluation and urinary pregnancy test
- Administration of study medication
- 4-hour clinical observation:
 - Vital signs and observation of the injection site 1, 2 and 4 hours after the administration of study medication
 - Physical examination before discharge

3.5.2.17 Phone call 4 [Week 48]

- AEs
- Concomitant medications (describe new and/or changes from the previous visit)
- In case of safety concerns, as per investigator assessment, an additional visit will be scheduled in order to further assess the event(s).

3.5.2.18 Visit 9 [Week 50]

This visit can take place within a period of up to 2 days.

- AEs
- Concomitant medications (describe new and/or changes from the previous visit)
- Physical and neurological examination
- Vital signs
- Cognition: RBANS (form A)
- Clinical status: CDR, NPI, C-SSRS
- Blood sample collected for:
 - routine hematology and biochemistry evaluation, including CRP
 - antibody response components including for example anti-pTau and anti-Tau IgG and IgM titers
 - Inflammatory cytokines
 - AD biomarker assessment
 - T-Cell profile assessment
 - ANA and anti-dsDNA testing
- Lumbar puncture for cerebrospinal fluid sample (12 mL) for cell count, inflammatory markers and exploratory biomarker testing (note: blood for serum albumin should be taken and measured concomitantly)
- Routine urine evaluation
- ECG
- Brain MRI

3.5.2.19 Visit 10 [Week 67]

- AEs
- Concomitant medications (describe new and/or changes from the previous visit)
- Physical and neurological examination
- Vital signs
- Blood sample collected for:
 - routine hematology and biochemistry evaluation, including CRP
 - antibody response components including for example anti-pTau and anti-Tau IgG and IgM titers
 - Inflammatory cytokines

AD biomarker assessment ANA and anti-dsDNA testing

3.5.2.20 Visit 11 [Week 74]

This visit can take place within a period of up to 2 days.

- AEs
- Concomitant medications (describe new and/or changes from the previous visit)
- Physical and neurological examination
- Vital signs
- Cognition: RBANS (form B)
- Clinical status: CDR, NPI, C-SSRS
- Blood sample collected for:
 - routine hematology and biochemistry evaluation, including CRP
 - antibody response components including for example anti-pTau and anti-Tau IgG and IgM titers
 - Inflammatory cytokines
 - AD biomarker assessment
 - ANA and anti-dsDNA testing
- ECG
- Brain MRI

3.5.2.21 Visit 12 [Week 86] (Optional)

This visit would be applicable for future or ongoing sub-cohorts where the sponsor is interested in extending the post-injection follow-up period and where subjects have not yet passed study visit 12 (week 86). Prior to any assessment described below, written consent of subjects will be obtained, and in the Netherlands, the subjects' decisional capacity will be re-assessed before consenting.

If feasible, after subject consent and if locally permitted, this visit may also be performed at subject's home.

- AEs
- Concomitant medications (describe new and/or changes from the previous visit)
- Blood samples collected for:
 - antibody response components including for example anti-pTau and anti-Tau IgG and IgM titers
 - AD biomarker assessments

3.5.2.22 Visit 13 [Week 98] (Optional)

This visit would be applicable for sub-cohorts where the post-injection follow-up period has been extended. Prior to any assessment described below, written consent of subjects will have been obtained, and in the Netherlands, the subjects' decisional capacity will have been re-assessed before consenting.

If feasible, after subject consent and if locally permitted, these visits may also be performed at subject's home.

- AEs
- Concomitant medications (describe new and/or changes from the previous visit)
- Blood samples collected for:
 - antibody response components including for example anti-pTau and anti-Tau IgG and IgM titers
 - AD biomarker assessments

3.5.2.23 Unscheduled Visit (UV)

At any time during the study, subjects might be invited to the site for additional visits (e.g. further evaluation needed following a phone call with the subject). In case of safety concerns, as per investigator assessment during a scheduled "Phone call" or a visit of the post-injection period extension (if applicable) with the subject, an additional visit will be scheduled in order to further assess the event(s). Any subjects attending an unscheduled visit should at a minimum complete the following safety related assessments:

- Provide information on new AEs/SAEs since last visit.
- Provide information on new concomitant medication since last visit.
- Be examined for the Vital signs
- Go through physical and neurological examination
- Have blood withdrawn for standard safety evaluation

Upon investigator's medical judgement, other assessments considered as needed can be performed during those visits (MRI, ECG, etc.).

Due to the resurgence of the pandemic in multiple participating countries since September 2020 and in case the subject and caregiver cannot travel to the site due to Covid-19 restriction, the Unscheduled Visit and related assessments will be performed at subject's home if feasible and locally permitted (see details under 3.5.1.1 Alternative Mode of Administration of Assessments to Reduce Safety Risks due to Participation during Covid-19 pandemic).

3.5.3 Assessments for Premature Termination

Any subject, who withdraws from the study prior to completion (see standard categories of early termination under section 3.3.3), will be encouraged to at least complete the safety assessment evaluation (see detail under 3.5.2.21 Unscheduled Visit) by attending a last visit.

If this is not possible, subject will be asked to at a minimum, provide the reason for withdrawal and provide information on any adverse events that might have arisen since the last visit and the outcome of any previously recorded AEs.

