5.3.6.2 Analysis of Primary Endpoint

Geometric mean and change from baseline at Visit 9 [Week 50] in Anti-pTau IgG titer will be calculated. The response will be defined using the parameters given in the SAP. Time-dependent development of the titers will be displayed graphically per dose group and per subject.

The number and proportion of subjects with a positive response will be summarized per visit and per dose group. The determination of negative/positive response will be done using a threshold defined during assay validation. Response rates will be displayed graphically in a response rate vs. dose plot to investigate whether there is any dose response relationship.

In addition, the peak and area under the curve of antibody response will be described. The results will be summarized per dose group.

No statistical testing has been planned for antibody responses.

During interim reviews, similar analyses will be performed up to the relevant visit as specified in section 5.3.8.

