6.3 Discontinuation of the Study by the Sponsor

Should it prove necessary to discontinue the study permanently prior to completion (e.g. for compromised safety), subjects will be examined as per the final visit and appropriate early study completion CRFs completed.

In case it is decided to terminate the study prematurely, the sponsor will immediately notify investigators, relevant authorities and additional contacts. Investigators will promptly notify their relevant Ethics Committees and the study participants. The study products and materials will be returned.

In the Netherlands, based on Article 3 of the Revised CCMO Directive on the Assessment of Clinical Trial Agreements dated 1 November 2011, premature termination is only possible:

- a. if the judgement of the competent medical research ethics committee that has assessed the study is irrevocably revoked;
- b. if a reasonable case can be made for terminating the study in the interests of the health of the research subjects;
- c. if it transpires that continuation of the study cannot serve any scientific purpose, and this is confirmed by the medical research ethics committee that has issued a positive decision on the study;
- d. if one of the parties or the funder has been declared insolvent or a bankruptcy/windingup petition has been filed in respect of one of the parties or the financier, or one of the parties or the financier is dissolved as a legal entity;
- e. if the principal investigator is no longer capable of performing the tasks of the principal investigator, and no replacement agreeable to both parties can be found;
- f. if one of the two parties fails to comply with the obligations arising from the agreement and, provided compliance is not permanently impossible, this compliance has not taken place within thirty days of the defaulting party receiving a written request to comply, unless failure to comply is not in reasonable proportion to the premature termination of the study;
- g. if circumstances beyond the control of the sponsor, investigator or funder make it unreasonable to require the study's continuation.

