### **11.5.8 Cognitive/Clinical Variables**

The following cognitive/clinical assessments will be conducted for this study:

[figure not shown]
- CDR-SB (Clinical Dementia Rating Scale-Sum of Boxes) at visits: Screening (applicable to all subjects except those in Sub-cohort 1.1 and those enrolled prior to Protocol v4.0), Visit 1 (Week 0) (only applicable to sub-cohort 1.1 and to patients enrolled prior to protocol v4.0 being locally approved), Visit 6 (Week 26), Visit 9 (Week 50) and Visit 11 (Week 74). The baseline value is the score obtained at Screening except for subjects of sub-cohort 1.1 and to patients enrolled prior to protocol v4.0 being locally approved for which the baseline value is the score obtained at V1 [Week 0]. For other endpoints, the baseline value is the score obtained at V1 [Week 0].
- RBANS (Repeatable Battery for the Assessment of Neuropsychological Status) at visits: Screening, Visit 1 (Week 0), Visit 6 (Week 26), Visit 9 (Week 50) and Visit 11 (Week 74). Three versions of the scale are used during the study: form A (at V1 and V9), form B (at V6 and V11) and form C (at Screening).
- Mini Mental State Examination (MMSE) at Screening only
- NPI (Neuropsychiatric Inventory Scale) at visits: Visit 1 (Week 0), Visit 6 (Week 26), Visit 9 (Week 50) and Visit 11 (Week 74)
- Columbia-Suicide Severity Rating Scale (C-SSRS) at visits: Screening, Visit 1 (Week 0), Visit 6 (Week 26), Visit 9 (Week 50) and Visit 11 (Week 74)
- MacCAT-CR (MacArthur Competence Assessment Tool for Clinical Research, applicable only to subjects from the Netherlands) at visits: Screening, Visit 5 (Week 24) and Visit 8 (Week 48)

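### The exit visit for study withdrawals is cited by the wrong section number and requires no C-SSRS, so most subjects who withdraw before Week 26 have no planned post-dose suicidality rating

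*Protocol*

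**What the plan says.** Protocol 3.3.3 refers to 3.5.3 for the assessments due when a subject discontinues. Section 3.5.3 says that such a subject "will be encouraged to at least complete the safety assessment evaluation (see detail under 3.5.2.21 Unscheduled Visit) by attending a last visit". If that cannot be done, the site asks at least for the reason for leaving and for adverse events.

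The section with the cited number has a heading that begins "3.5.2.21 Visit 12 [Week 86] (Optional". The visit named in the label stands two sections later, under a heading that begins "3.5.2.23 Unscheduled Visit (UV". Its minimum list covers adverse events, concomitant medication, vital signs, physical and neurological examination, and one blood item: "Have blood withdrawn for standard safety evaluation". Other assessments may be added if the investigator judges them necessary.

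Suicidal ideation by C-SSRS and anti-pTau IgG titer are both primary endpoints (Protocol 2.2.1, SAP 7.1). SAP 11.5.8 schedules the scale as "C-SSRS) at visits: Screening, Visit 1 (Week 0), Visit 6 (Week 26" and continues with Weeks 50 and 74. Protocol 5.3.5.1 makes the Visit 1 value the baseline for every such scale except CDR-SB.

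If the sponsor stops the study, Protocol 6.3 applies a different rule: "subjects will be examined as per the final visit and appropriate early study completion CRFs completed".

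**The concern.** Section 3.5.3 is the only place that defines the exit assessments, and its number and label disagree. A site that follows the number finds a visit with antibody blood but no vital signs, examination or safety laboratory. A site that follows the label finds the safety items but no titer. Neither finds a C-SSRS.

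The C-SSRS matters most. The scale is sparse after dosing, so a withdrawal in the first half year can leave a dosed subject with no structured suicidality rating after baseline. In an initial sub-cohort with 6 subjects on active vaccine, one such subject is 1/6 = 17% of the dose group. Blood is already being drawn at the exit visit, so the missing titer could also be avoided cheaply.

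**Working it through.** The plan states no figure on this point, and no test depends on it ("No statistical testing has been planned for antibody responses", Protocol 5.3.6.2). The check sets the candidate visits side by side and counts scheduled assessments.

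**Content of the visits** (Protocol 3.5.2.20, 3.5.2.21 and 3.5.2.23):

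| Item | 3.5.2.21, Visit 12 (cited number) | 3.5.2.23, Unscheduled Visit (cited label) | 3.5.2.20, Visit 11 (final visit, via 6.3) |
|---|---|---|---|
| AEs, concomitant medication | yes | yes | yes |
| Vital signs, physical and neurological examination | no | yes | yes |
| Safety blood | no | yes | yes |
| Antibody titers | yes | not in minimum | yes |
| C-SSRS | no | not in minimum | yes |

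**C-SSRS before Week 26.** Injections are at Weeks 0, 8 and 24 (Protocol 3.4.2), so up to 3 precede Week 26. Ratings are at Screening and Weeks 0, 26, 50 and 74, and Week 0 is baseline. Planned post-dose ratings before Week 26: 0. The first comes 26 − 0 = 26 weeks after the first injection.

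**Exception.** For 7 of 8 sub-cohort 1.1 subjects, Visit 5 became a telephone interview at Week 24 ± 7 days that included the C-SSRS where possible (Protocol 3.5.2.10, SAP 12.0). That gives at most one rating before Week 26, and only to those still in the study at that interview. The third injection was not given to these seven.

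**Titers.** With the added visits, samples fall at Weeks 0, 2, 8, 10, 15, 20, 24, 26, 31, 36, 42, 48, 50, 67 and 74 (SAP 11.6.1).
- Post-dose samples before Week 26: 6 (Weeks 2, 8, 10, 15, 20, 24), or 4 without Visits 4.1 and 4.2.
- Longest gap up to Week 50: 6 weeks (for example 48 − 42). Without the added visits it is 24 − 10 = 14 weeks.
- Longest gap after Week 50: 67 − 50 = 17 weeks.

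These are gaps on the planned schedule. For the seven subjects whose Weeks 24 and 26 were remote, the gap was 36 − 10 = 26 weeks or more if they also had none of the added visits.

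**Who is affected.** Subjects who only stop the vaccine are followed on site 19 and 26 weeks after the last dose (Protocol 3.2.3). That is Weeks 19 and 26 after one dose, 27 and 34 after two, and 43 and 50 after three. If the second of these mirrors Visit 11, it carries a C-SSRS. The gap therefore concerns withdrawal from the study.

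**Sponsor termination.** Protocol 3.3.3 gives termination by the sponsor as an example of an early-termination reason, and 3.5.3 applies to those reasons. Section 6.3 calls for the final-visit examination. The same subject falls under both rules.

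**Use of an exit sample.** SAP 8.12 maps an unscheduled assessment to a planned visit only if it lies inside that visit's window, and otherwise lists it. SAP 8.21 defines peak as the highest post-dose value and does not mention exit samples.

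**The case against.** The numbering error will probably mislead few sites. Section 3.5.3 speaks of a safety evaluation and names the Unscheduled Visit, and only one section has that title. Visit 12 needs separate consent and belongs to an optional extension. This largely stands: loss of safety data by following the number is possible but unlikely.

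A reader might infer that early leavers have no exit titer. The documents do not support that. Section 3.5.3 sets a floor, 3.5.2.23 allows additions, and Protocol 3.5.5 and SAP 11.6 say that immune-response blood is taken at all visits, without saying whether an exit visit counts. The accurate statement is that the labelled visit does not require a titer. Scheduled sampling is frequent, so little is lost, and an off-window exit value would not reach the by-visit tables.

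A reader might also infer that anyone leaving before Week 26 lacks a rating. The sub-cohort 1.1 interview and the continued follow-up of subjects who only stop the vaccine rule that out.

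It is also fair that the C-SSRS gap comes from the schedule as much as from 3.5.3, that suicidal events reported as adverse events are still collected at exit, and that attendance is only encouraged. An exit C-SSRS would help only leavers who attend. These points limit the gap. They do not supply a required rating.

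**Conclusion.** The point holds in limited form. The reference in 3.5.3 is wrong. Under either reading the exit visit requires no C-SSRS, and outside the sub-cohort 1.1 remote interview a study withdrawal before Week 26 has no planned post-dose rating on a primary safety endpoint. For titers the loss is confined to the interval since the last scheduled sample.

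How many subjects this affects cannot be derived from the documents. In the preceding study 2 of 24 subjects discontinued (Protocol 1.1.2.3). If that rate is assumed, the chance of at least one leaver at any time is 1 − (22/24)^6 = 41% among 6 active subjects and 1 − (22/24)^18 = 79% among 18. A reader might take these as the chance of an unrated subject. They are not: the timing of those two discontinuations is not given, and neither is the share of leavers who attend a last visit. Nor do the documents show that leavers differ in response, since both earlier discontinuations were attributed to an unrelated medical condition.

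This is a cheap improvement that recovers primary safety data. It does not threaten the study's conclusions.

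**What to change.** In Protocol 3.5.3, cite 3.5.2.23 and list the exit assessments: the Unscheduled Visit minimum, the C-SSRS Since Last Visit form (which SAP 11.5.8.5 assigns to every visit after Screening), and one serum tube for antibody titers taken in the safety draw. Reconcile 3.3.3 and 3.5.3 with 6.3 on which assessments apply when the sponsor stops the study.

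In the SAP, state that an exit C-SSRS enters a summary of ratings at any time after dosing. State also that an off-window exit titer enters the listing and the peak but not the by-visit tables, consistent with 8.12. If subject visits are already complete, this SAP wording can still be added and applied to any exit data that were collected.

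The cost is some wording, a short rating and one more set of titer assays for each leaver who attends. The rating needs a trained clinical rater (Protocol 3.5.4), whom sites already have but whom the Unscheduled Visit minimum does not call on. The assays go to the immunogenicity vendor. No extra visit is needed.
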